covered in this IND application. That IRB trial would allow up to five years follow up on subjects and would only allow investigators to observe how the subject is doing long term, whichever treatment options the subject pursues in consultation with their regular doctor in that time. That planned follow up protocol will allow Stanford to contact the subjects several times a year in order obtain information about any therapy they may elect to follow, including sildenafil if their regular doctor prescribes it, and their response to any therapy.

Multi-Center:

Yes

Number of Centers:

Up to 4

Blinding:

|                |     |
|----------------|-----|
| Observer-Blind | Yes |
| Subject-Blind  | Yes |
| Double-Blind   | Yes |

Randomization:

Group Assignment Ratio: 2:1 randomization of two subjects who receive sildenafil to one subject who receives placebo.

Concurrent Control:

No other treatments for lymphatic malformation will be allowed except antibiotics and/or surgical drainage if the lesions become infected. Treatment for recurrent infections in the lymphatic malformation will be allowed and documented during the trial. Concurrent medications will be documented. Subjects who require sclerosing agents or excisional surgery of their lymphatic malformation will be withdrawn from the trial.

Variable(s): PRIMARY: Change in lesion volume over twenty weeks of the test medication as evaluated by MRI examination. Comparison of placebo to sildenafil treated subjects.

SECONDARY: Change in lesion volume estimated using a soft tape measure to measure the length, width, and hemispheric measurement of each of the lymphatic malformations. (Berk, Berk et al. 2011) Completion of the form *Lymphatic Malformation Measurements*.

Subject's evaluation of the change in lesion clinical characteristics from baseline to 20 weeks by examining decreased discomfort, texture or thickness, distortion of normal anatomy or overall change obtained in the subject's

completion of *Subject's Assessment of Lymphatic Malformation Change* form.

Physician's evaluation of the lesion clinical characteristics on the day of the visit. This includes color, tenseness and texture, superficial component, deep component, and distortion of anatomical landmarks. This requires completion of the *Lymphatic Malformation Assessment* form for each LM site.

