Physician's evaluation of the change in lesion clinical characteristics from baseline, such as change in texture or thickness, change in distortion of normal anatomy, and over change in lesions. This requires completion of the *Lymphatic Malformation Assessment of Change* form for each LM site.

Comparison of LM volume from MRI assessment to Body Surface Area (BSA) measurements before and after 20 weeks of sildenafil.

Blinded physician observer scored evaluation of clinical photographs taken prior to the initial dose of sildenafil or placebo and at the 20 week visit prior to the unblinding. Subjects who receive placebo and then enter the 20 week open label continuation will have additional photographs taken after 20 weeks of sildenafil.

Presence, frequency or absence of infection during trial.

Relationship of response to sildenafil to previous infections, sclerotherapy or surgery.

**SAFETY:** Adverse events and frequency of lesion infections.

Adverse Events: Both volunteered and elicited.

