### 3. INTRODUCTION

#### 3.1. BACKGROUND

**Lymphatic malformations** (LMs) are uncommon, congenital vascular anomalies that arise due to developmental dysplasia of the lymphatic network in utero.(Blei 2008) LMs are equally rare independent of sex or race.(Redondo, Aguado et al. 2011) About 65% of LMs are detected at delivery, 80% by 1 year of age, and 90% by 2 years of age

emphasizing their childhood expression.(Redondo, Aguado et al. 2011) The deeper ones may not be initially noticed but will become recognized as they increase in size or become infected. Although histologically benign, they are often locally invasive and affect the skin and soft tissues, as well as nerve, muscle or bone in some cases. Cystic hygromas are a specific type of congenital malformations of the lymphatic system that are commonly on the posterior neck. (Gallagher, Mahoney et al. 1999) They occur in about one in 1,775 live births (Howarth, Draper et al. 2005) to one in 2667 live births (Fisher, Partington et al. 1996) making them truly an orphan disease. The incidence may be higher as they can be associated with other fetal abnormalities resulting in spontaneous or induced abortions.(Fisher, Partington et al. 1996) In one series of 17 live born infants with cystic hygroma, 15 survived the first year of life yielding a survival rate of 88%.(Fisher, Partington et al. 1996) Lymphatic malformations often have considerable morbidity, associated with infection, bleeding and airway or vision obstruction as well as significant psychosocial concerns. (Greene, Perlyn et al. 2011) When present on the extremities, they often bleed with physical activity, may inhibit movement and ambulation, and are at times painful.

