A second method to evaluate the volume of the MRI will be done in a blinded manner by a pediatric radiologist, assisted by a pediatric radiology fellow. We will use segmentation to identify the surface area demonstrating LM involvement of multiple planes though the lesion. By calculating the surface area of multiple planes and knowing the distance between planes, the volume of the LM can be calculated. This is called segmentation analysis. The research radiologist and fellow will evaluate multiple MRIs in groups at the same time, unaware of the date or the subject, therefore blinded to treatment, placebo, or pretreatment. This evaluation will be blinded in order to eliminate the bias of knowing who the subject is in the study. Although this is a research procedure, the results will be reported in the subjects Radiology Report in the Medical Record as an addendum. It will be signed by the research radiologist. This evaluation will be available several weeks after the subject completes the 20 weeks of sildenafil and/or placebo. The MRI will be read and the data recorded by the research radiologist without knowledge of the date the MRI was done. Once the data is collected and recorded, the research radiologist will learn name of the subject and the date of the MRI in order to attach the correct volume calculation to the correct MRI when placing the volume data in the Medical Record.

The volume data on the subject's LM(s) relative to the subject's BSA will then also be evaluated for any changes. Since all subjects will be children under 10 years old, using the BSA measurement may help to adjust our volume assessment to accommodate the amount that a subject has grown over the course of the course of treatment.

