### 7.4.4. Photography methods

The digital photographs of each lymphatic malformation in this study will be acquired by the site investigators. The investigators will be fully trained in the standardized acquisition procedures. At least two digital photographs of the lymphatic malformation will be acquired for each subject at the baseline visit and the 20 week visit. Photographs may be taken at other visits but they will not be part of the final analysis. The first photograph will be taken with the image plane parallel to the lymphatic malformation (front-on view) and the second photograph will be taken with the image plane at a different angle to that of the first photograph (side-on view) so that the thickness of the lesion can be clearly visualized. The subject will be sitting on a chair while photographs are taken. If subject is an infant, subject's parent or guardian will be sitting on a chair with the infant sitting on his/her knees, if possible, or in his/her arms. In the field of view, all photographs will include a color chart for color and size calibration. Patient identification information, date of the photograph and therapy information will not be visible on the photograph. For each photograph acquisition, the color chart will be held in the same plane as the lymphatic malformation. The photographs will be acquired at a fixed distance from the patient at two different angles defined at baseline (one for Photograph 1 and one for Photograph 2).

The photographs will serve the following purposes:

- 1: To identify the lymphatic malformation or malformations if the subject has more than one malformation.
- 2: To qualitatively assess lymphatic malformation evolution between visits and to quantify the size and the color of the lymphatic malformation at baseline and Week 20.

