#### **10.2.2. Secondary Efficacy**

The secondary efficacy variables will be change from baseline and at visits four weeks twelve weeks, twenty weeks and 32 weeks.

These will include the changes in the soft tape measurements of the lesion by comparing the measurements of length, width, and hemispheric measurement. The volume of the lymphatic malformation will be estimated based on these measurements.

Statistical analysis of the *Subject's Assessment of Lymphatic Malformation Change* form. This will give data on the subject's evaluation of the change in lesion clinical characteristics from baseline, such as decreased discomfort, texture or thickness, distortion of normal anatomy or overall change by correlating the data obtained in the subject's completion of *Subject's Assessment of Lymphatic Malformation Change* form.

Statistical analysis of the *Lymphatic Malformation Assessment* form for each LM site. This will give data on the physician's evaluation of the lesion clinical characteristics on the days of the visits. This includes color, tenseness and texture, superficial component, deep component, and distortion of anatomical landmarks.

Statistical analysis of the *Lymphatic Malformation Assessment of Change* form for each LM site. This will give data on the physician's evaluation of the change in lesion clinical characteristics from baseline, such as change in texture or thickness, change in distortion of normal anatomy, and over change in lesions.

Change in LM volume from MRI assessments in relation to BSA will also be carried out. REDCap calculates the BSA from height and weight measurements at each visit. Since growth can be non-linear, relating the LM volume to a subject's BSA may help to explain why a small change to the LM (by MRI volume analysis) is assessed as moderate by the investigator and parents of the subject (i.e., the LM may have stayed the same size but the child grew quickly, so the LM appears smaller by visual assessment).

The digital photographs of each lymphatic malformation in this study will be acquired by the site investigators. At least two digital photographs of the lymphatic malformation will be acquired for each patient at each scheduled study visit, a front-on view and a side-on view. See Section 7.4.4. The clinical photographs evaluated by blinded observers in a blinded manner by physicians not associate with this trial. The observers of the

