photographs will compare the baseline photographs and score the additional visits as worse, no change, 1-25%, 26-50%, 51-75%, 76-100% improvement. We will also examine the potential value of 3D photography during the Baseline, 20 Week and 20-A Week visit.

Presence, frequency or absence of infection during trial will be documented.

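### The blinded photograph scale puts all worsening in one category, which costs sensitivity if placebo lesions visibly grow but does not favour sildenafil

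*Combined protocol and SAP*

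**What the plan says.** Section 10.2.2 (Secondary Efficacy) describes the reading as "The clinical photographs evaluated by blinded observers in a blinded manner by physicians not associate with this trial". The observers take the baseline photographs as reference and "score the additional visits as worse, no change, 1-25%, 26-50%, 51-75%, 76-100% improvement". That makes six ordered levels: one for any worsening, one for no change and four for improvement. No other section grades worsening on this scale.

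The Synopsis lists the reading among the secondary variables: "Blinded physician observer scored evaluation of clinical photographs taken prior to the initial dose of sildenafil or placebo", and again at the 20-week visit before unblinding. Placebo subjects who go on to open-label sildenafil are photographed again after 20 weeks of active drug.

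The plan assigns no numeric codes to the categories. It names no test or responder cut-off for them, does not say that scores will be averaged, and does not give the number of observers. Section 11 says that no effect size could be estimated.

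On the course of the disease, section 3.1 says that deeper lesions may go unnoticed at first but "will become recognized as they increase in size or become infected". It gives no rate of growth.

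**The concern.** A scale this uneven can describe degrees of benefit but not degrees of harm or progression. If sildenafil works partly by holding back growth, the contrast between the arms lies on the side of the scale that has been collapsed. A placebo lesion that grows a lot and a sildenafil lesion that grows a little are both recorded as 'worse', and the difference is lost.

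This matters because the photographs are the clinical assessment read by physicians outside the trial; the other clinical ratings come from subjects and investigators. Detail lost at scoring cannot be recovered in the analysis without reading the photographs again.

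**Working it through.** The plan states no figure for this endpoint, so there is nothing to reproduce. The check uses the stated categories and assumed inputs.

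**Inputs from the documents.** Six categories (10.2.2). Allocation is "2:1 randomization of two subjects who receive sildenafil to one subject who receives placebo" (Synopsis), with 60 subjects to be enrolled (6.1), hence 60 × 2/3 = 40 on sildenafil and 60 × 1/3 = 20 on placebo. The completer goal of forty in section 5.1 would give fewer per arm and lower power on either scale.

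**Assumptions, not in the documents.** Perceived percent change is normal, with positive values meaning improvement and the same SD in both arms. Changes within ±5 points are scored as no change. The test is a two-sided rank-sum test at 5%. The mirrored scale has worsening bands of 1-25%, 26-50%, 51-75%, 76-100% and over 100%.

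**Step 1: power, planned scale v mirrored scale (simulation).**

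| Placebo mean change | SD 30, true difference 25 | SD 20, true difference 17 |
|---|---|---|
| -30 points | 67% v 83% | 55% v 84% |
| -10 points | 78% v 82% | 79% v 83% |
| 0 | 82% v 84% | 80% v 81% |

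Repeat runs of the same model differ from these by 1 to 3 points, so gaps of one or two points are within simulation error.

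**Step 2: where the loss comes from.** Code the planned scale -1 to 4 and a nine-level symmetric scale -4 to +4. With SD 20 and the sildenafil mean at 0, the expected difference between arms is:

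- placebo -10: 0.44 step planned, 0.57 symmetric
- placebo -25: 0.88 v 1.37
- placebo -50: 1.09 v 2.47

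The placebo mean on the planned scale is -0.77 at -25 and -0.98 at -50. It runs into the floor at -1, and further growth adds almost nothing to the contrast.

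**Step 3: no true change.** With the mean at 0, the chance of 'worse' equals the chance of any improvement (0.401 each at SD 20), so these two cancel in a mean score. What is left is

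mean score = P(X > 25.5) + P(X > 50.5) + P(X > 75.5).

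- SD 10: 0.005 + 0.000 + 0.000 = 0.005 step
- SD 20: 0.101 + 0.006 + 0.000 = 0.107 step
- SD 30: 0.198 + 0.046 + 0.006 = 0.250 step

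The median stays at no change throughout. Comparing two arms of 40 and 20 drawn from this same distribution at SD 30, the mean difference was -0.003 and the Welch test rejected in 5.1% of 20,000 runs, which is its nominal level.

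**The case against.** The strongest objection is that the loss depends on inputs nobody knows. Section 3.1 explains why deep lesions are found late; it does not say that lesions grow visibly in 20 weeks. The large losses need a placebo mean well below zero. With no placebo growth the two scales perform alike. Where power is near its ceiling, the loss is small even with heavy growth: at SD 20, difference 25 and placebo -30, power is 93% v 99%. This stands, and it is why the result is a range. It also works the other way: at SD 15, difference 12 and placebo -30, power is 24% v 73%.

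Growth is also measured elsewhere. MRI volume is the primary endpoint (10.2.1), tape-measured volume is secondary (10.2.2), and section 7.4.4 intends the photographs "to quantify the size and the color of the lymphatic malformation at baseline and Week 20". The study calls itself exploratory. This stands and limits the importance of the point.

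Three stronger readings are tempting, and the documents do not support them:

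- **That the scale favours sildenafil.** Compressing placebo growth shrinks the difference. With equal rating noise in the two blinded arms, no false difference arises (step 3).
- **That rating noise will show up as improvement.** This needs numeric codes and a mean, which the plan does not specify, and noise wide enough to cross a 25-point band.
- **That knowing which photograph is baseline biases the comparison.** The MRI reader is "unaware of the date or the subject, therefore blinded to treatment, placebo, or pretreatment", and the photograph observers do know which picture is the reference. But they are blind to arm, section 7.4.4 keeps date and therapy off the image, and knowledge of order is common to both arms. The plan's own remark that "the LM may have stayed the same size but the child grew quickly, so the LM appears smaller by visual assessment" likewise applies to both arms.

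**Conclusion.** The point holds as a limitation of a secondary endpoint. All worsening receives one score, so the scale loses sensitivity if placebo lesions visibly worsen. Under the assumptions shown, the loss in power runs from 1 or 2 points with no placebo growth, through about 4 points at a mean worsening of 10, to 16 points (SD 30) or 29 points (SD 20) at a mean worsening of 30. These figures rest on a normal model, equal SDs, full enrolment and assumed effect sizes. The documents cannot say which row of the table applies.

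The direction is conservative for the randomized comparison. An upward shift in the mean under no change arises only if categories are coded and averaged. It would then matter mainly for statements within one arm, above all the photographs after open-label sildenafil (Week 20-A), which have no concurrent control.

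**What to change.** In section 10.2.2, divide 'worse' into 1-25%, 26-50%, 51-75%, 76-100% and more than 100% worse, and leave no change and the four improvement bands as they are. Keep baseline as the reference photograph. State that the arms will be compared with an ordinal, rank-based test and not by a mean score. For the Week 20-A photographs, report the distribution across categories.

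Do not present the pairs in shuffled order and restore the direction afterwards. Percent change is not symmetric when a pair is reversed: a 40% reduction read backwards is a 67% increase (1/0.60 = 1.67), and a 60% reduction is a 150% increase (1/0.40 = 2.50). The same lesion would fall in different bands depending on the order shown.

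The cost is a revised scoring sheet and four more categories for the observers. The photographs and observers stay the same, and the mirrored scale did not materially lower power in any scenario run.

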#### **10.2.3. Exploratory Efficacy**

Not applicable.

### **10.3. SAFETY**

All subjects who receive study medication will be evaluable for the safety analysis. Summary statistics will be provided with respect to patients requiring discontinuation from treatment and from study (any reason and for safety reasons). AE summaries will focus on treatment-emergent AE and will summarize subject AE incidences by severity, seriousness, and relationship to treatment. Vital signs, laboratory tests, and concomitant medication usage will be displayed as listings by subject.

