## 2. SYNOPSIS

Study Phase: 2

Financial Disclosure Information for U.S. FDA Submission to be Obtained? Yes

Test Medication: Sildenafil 20 mg tablets, 2.5mg/ml suspension (Revatio®)  
Control Medication: Placebo tablets or suspension resembling Revatio®

Study Dosage / Usage: Oral dosage of sildenafil. For pediatric patients 8 kg to 20 kg the suspension/tablets dose will be 10 mg/4ml three times a day (30 mg per day) and for patients > 20 kg the dose is 20 mg/8ml three times a day (60 mg a day). Subjects less than 8 kg will not be enrolled in the trial.

Route of Administration: The medication will be given orally. The subjects who will receive the 10 mg dose will be given an oral suspension (using dose calculation by the study pharmacist) or half a tablet. Subjects will have the option of taking tablets or receiving an oral suspension of the medication in 2.5mg per mL.

Objective(s): The objectives of this study are to assess the safety and effectiveness of sildenafil taken orally to improve or resolve lymphatic malformations.

Study Population: Sixty Subjects (60)

Subjects will be between the ages of 6 months to 10 years of age inclusive with lymphatic malformations (LM) that have a **minimum diameter of 3 centimeters** based upon MRI evaluation. Based on the patient numbers in pediatric dermatology clinics over the country, we expect that we will be able to screen 60 patients who will meet the inclusion criteria, and 55 patients will be enrolled in the study and begin medication. After 15 subjects are completed, an interim analysis will be performed to project effect size and estimate the total number of subjects required for the study. If after analysis of 15, 30 or 45 subjects we find that we are in the range of futility or efficacy, then we will notify the FDA as well as the DSMB, and begin to end the study by adding no additional subjects.

Structure: Double-blind trial of placebo compared to sildenafil with an open label extension for subjects who received placebo. Two to one ratio of two sildenafil treated subjects who

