receive active sildenafil to one placebo treated subject. During the twenty week evaluation visit, after completion of all evaluations, the randomization code will be broken and both the subject and investigator will know the results. The subjects who have randomized to placebo will have the option to begin a twenty week course of sildenafil. If the subjects who were on placebo elect to take active drug, the initiation visit can be completed at that time. The subject will then be followed with clinic visits at weeks 4, 12, 20 and 32 as indicated in the protocol. We will call the subjects at weeks 2, 8 and 16 to inquire about any questions that the subjects may have or any concerns. We will also request information on medication taken and their progress.

The subject's LMs will be categorized by the Pediatric Radiologist by the percent of the LM that is microcystic. Upon completion of the initial 15 subjects, the data will be evaluated in an interim analysis in order to determine if the percent of macrocystic component of the lesions suggests which subjects may have the best benefit. The initial 15 subjects will also be evaluated related to previous procedures, infections and other complications related to their lymphatic malformations. If specific characteristics of the LM are identified that suggests beneficial effect of the sildenafil, the protocol will be changed to enroll those subjects who are projected to have the best benefit. A new power analysis will be done to project the minimum numbers of subjects that should be enrolled further in the study.

Duration of Treatment: 20 weeks. Placebo subjects will complete 20 weeks of placebo and then have an option for 20 weeks of active sildenafil.

Duration of Assessment: The subjects will be evaluated for 20 weeks on therapy then followed for 12 weeks off therapy.

Open Label Extension: Placebo subjects will have an option to enter an open label treatment after they have completed 20 weeks of placebo.

Duration of treatment: Placebo 20 weeks  
Washout Between Periods: none  
Duration of Treatment: 20 weeks on active drug

After the completion of 20 weeks of sildenafil and 12 weeks of follow up, the subjects will have the option to be followed through an IRB approved long-term follow up trial not

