## **6. STUDY DESIGN**

### **6.1. STUDY DESIGN**

**Figure 6.1-1: Study Design Schematic.** Decision points are indicated in bold text. Treatment periods are indicated. Double lined boxes indicate visits that will occur at the subject's closest site, whether at Stanford or at a Cooperating Research Site (Denver, Chicago, Kansas City).

CLINICAL PROTOCOL – Confidential

This will be a double blind placebo controlled trial with a ratio of 2 sildenafil subjects to 1 placebo subject in the Initial Treatment Period. Sildenafil or placebo will be given for 20 weeks.

60 research subjects will be enrolled.

There will be visits at Screening, Initial dose visit (includes a 2 hour observation period after initial dose), 4 weeks, 12 weeks, 20 weeks and 32 weeks visits. MRI examination will be part of the screening visit and will be repeated prior to the completion of medication at the 20 week visit. For subjects identified at Stanford, all visits will be conducted at Stanford University Medical Center. For subjects identified at other sites, all Screening, Initial Dose Visit, and Week 20 visits will be conducted at Stanford, including both MRIs. All other visits (weeks 4, 12, 32) will be conducted at the subject's local site. These subjects will be given the option to have the blood work for Screening done at their local site or at Stanford. They will also be given the option to have the eye exams and hearing exams at Screening and Week 20 done at their local site or at Stanford. Having these tests done locally at screening may make it easier to re-test if there is a change in vision or hearing while on sildenafil.

At the completion of 20 weeks of medication or placebo the subject will be evaluated by MRI, and will undergo an eye exam and a hearing exam. After the MRI, eye exam, and

hearing exam are completed, the subject will be evaluated by the investigator, and the subject will complete the self evaluation of response. The Investigator will complete the physician evaluation forms. After these evaluations are completed, the blind will be broken and the investigator and subject will know if the subject received placebo or sildenafil. The subject will also be informed of the of the MRI results of the screening MRI and the 20 week MRI once that report is available. Subjects who received placebo for the first 20 weeks will then have the option of starting 20 weeks on active drug.

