9. Completion of the physician's evaluation of the lesion clinical characteristics on the day of the visit. This includes color, tenseness and texture, superficial component, deep component, and distortion of anatomical landmarks. This requires completion of the *Lymphatic Malformation Assessment* form for each LM site.
10. Physician's evaluation of the change in lesion clinical characteristics from baseline, such as change in texture or thickness, change in distortion of normal anatomy, and over change in lesions. This requires completion of the *Lymphatic Malformation Assessment of Change* form for each LM site.
11. Collect study drug and perform compliance assessment; medication journal reviewed.
12. Obtain a pregnancy test if the subject is has achieved menarche.
13. The participant or parent/guardian and the investigator will complete the qualitative assessment of efficacy. The subject's evaluation of the response to the treatment will be reviewed. The results report of the MRI done at the twenty week visit will be shared with the subject and compared with the initial MRI reported results. After that discussion the subject will be told if they were on sildenafil or placebo. Subjects who received placebo will be given the option to start the sildenafil. Subjects who received active medication will be requested to stop the sildenafil for the next twelve weeks and follow up at the 32 week visit to examine the response of the lesion off of the sildenafil.

14. If subject received placebo and decides to receive sildenafil at this time, the study medication dose will be calculated and obtained from the pharmacy for adequate study medication to last until the next visit in 4 weeks. The 2 hour monitoring will be completed after the first dose as described in Baseline visit. For more detail, see Section 7.1.7. If the subject was on placebo and elects not to start sildenafil they will not need to return for the 32 week evaluation.
15. If the subject received placebo and decides to not receive sildenafil they will end the study at this time and complete additional information needed for the End of study 32 week visit described in 7.1.7. below.
16. If a subject approves, we will send a copy of the dictated record for the study visit to their local primary care doctor and /or pediatric dermatologist so that the physicians in their home community are aware of the study and the subject's participation in the study.

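### Section 10.3 plans only per-subject listings for vital signs and laboratory tests and names no arm or period for adverse events, so as written it gives no placebo-controlled view of blood pressure or laboratory change.

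*Combined protocol and SAP*

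**What the plan says.** The Synopsis makes safety a study aim: "The objectives of this study are to assess the safety and effectiveness of sildenafil taken orally". Section 6.1 sets the design: "This will be a double blind placebo controlled trial with a ratio of 2 sildenafil subjects to 1 placebo subject", and "60 research subjects will be enrolled".

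Section 10.3 then sets out three kinds of safety output.

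- Discontinuations: summary statistics, for any reason and for safety reasons.
- Adverse events: "AE summaries will focus on treatment-emergent AE and will summarize subject AE incidences by severity, seriousness, and relationship to treatment".
- Other measures: "Vital signs, laboratory tests, and concomitant medication usage will be displayed as listings by subject".

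It mentions neither arm, placebo, nor the blinded as against the open-label period. It has no entry for eye or hearing results. The relationship category in the adverse event summaries is the investigator's causality rating defined in section 12.5 (not related or possibly related); it does not stand in for the randomised arm. The Synopsis names adverse events and the frequency of lesion infections as the safety variables. It attaches the placebo comparison only to the primary efficacy variable. Sections 10.1 and 11 add no safety comparison.

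Follow-up differs by path. For sildenafil subjects: "The subjects will be evaluated for 20 weeks on therapy then followed for 12 weeks off therapy". For placebo subjects: "Placebo subjects will have an option to enter an open label treatment after they have completed 20 weeks of placebo". Under section 7.1.6: "If the subject was on placebo and elects not to start sildenafil they will not need to return for the 32 week evaluation".

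**The concern.** The protocol treats blood pressure, vision and hearing as matters to watch. Hypotension, or a risk of it, is an exclusion (section 5.3, item 2). Blood pressure is repeated every 30 minutes for 2 hours after the first dose (section 7.1.3, item 11), and families are told to report any change in vision or hearing (item 13). Laboratory, eye and hearing tests are scheduled at Screening and Week 20 (section 7.4.5 and Table 16-1).

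All of this is collected under blind in both arms, so the trial can show whether these measures move differently on sildenafil and placebo. A listing shows one child's values at a time. It gives no mean change, no spread and no contrast, and in growing children a change from baseline is hard to interpret without the concurrent control. If the arm and period of the safety tables are not fixed beforehand, they will be chosen after each subject's code has been broken at Week 20.

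**Working it through.** The plan gives no safety rate, SD, alpha or power, so there is no figure to reproduce. The check has a textual part and two illustrations.

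**1. What is collected against what is planned**

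| Measure | Collected in both blinded arms | Output in section 10.3 |
|---|---|---|
| Blood pressure, heart rate, oxygen saturation | Before dosing on Day 0; every 30 min for 2 h after the first dose; Weeks 4, 12, 20 (7.1.3, 7.1.5, 7.1.6) | Listing by subject |
| Laboratory tests | Screening, Week 20 (7.4.5) | Listing by subject |
| Eye and hearing tests | Screening, Week 20 (Table 16-1) | None |
| Adverse events | Throughout, with onset and resolution dates (12.1) | Incidence; arm and period not named |
| Discontinuations | Throughout (7.2) | Summary; arm and period not named |
| Lesion infections | During the trial (Synopsis, 10.2.2) | No separate output |

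For the first two rows the plan states a method, and that method contains no comparison. For adverse events and discontinuations it leaves arm and period open.

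**2. What a by-arm summary would give**

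Inputs: 60 subjects at 2:1 give 40 and 20 (section 6.1). The goal of forty completers (section 5.1) at 2:1 gives about 27 and 13. The SD is an assumption.

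95% half-width for a mean difference = t × SD × √(1/n₁ + 1/n₂).

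- 40 v 20: √(1/40 + 1/20) = 0.274; t(58) = 2.00; half-width 0.55 SD.
- 27 v 13: √(1/27 + 1/13) = 0.338; t(38) = 2.02; half-width 0.68 SD.

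| Assumed SD (mmHg) | 40 v 20 | 27 v 13 |
|---|---|---|
| 8 | ±4.4 | ±5.5 |
| 10 | ±5.5 | ±6.8 |
| 12 | ±6.6 | ±8.2 |

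For adverse event proportions, the half-width is 1.96 × √(p₁(1−p₁)/40 + p₀(1−p₀)/20). Assumed placebo and sildenafil rates of 5% and 20%, 10% and 30%, or 20% and 40% give about ±16, ±19 and ±23 percentage points.

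**3. Why period matters if adverse events are tabulated by arm**

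Follow-up is 20 + 12 = 32 weeks for sildenafil subjects, 20 for placebo subjects who decline drug, and 20 + 20 + 12 = 52 for those who cross over. Assume the same constant event rate in every arm and period, with incidence p at Week 20. Incidence by week w is then 1 − (1 − p)^(w/20). The last two columns are sildenafil minus placebo over the whole course, in points, when the true difference is zero.

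| p at 20 weeks | 32 weeks | 52 weeks | No crossover | Full crossover |
|---|---|---|---|---|
| 10% | 15.5% | 24.0% | +5.5 | −8.4 |
| 20% | 30.0% | 44.0% | +10.0 | −14.0 |
| 40% | 55.8% | 73.5% | +15.8 | −17.7 |
| 80% | 92.4% | 98.5% | +12.4 | −6.1 |

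The two ends partly cancel. At p = 40% and half crossing over, placebo incidence is (40 + 73.5)/2 = 56.8% against 55.8%, a gap of about −1 point. This table applies only if someone produced a by-arm, whole-course table, which section 10.3 does not state.

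**The case against.** A reader might infer that adverse events will be pooled across arms, or counted over each subject's whole course so that sildenafil events fall under placebo subjects. The documents do not support either reading. Section 10.3 is silent on arm and period. It directs the summaries to treatment-emergent events, which implies some exposure window even though the term is not defined. Onset dates are recorded (section 12.1) and open-label visits carry the -A suffix (Table 16-1), so a split by arm and period can still be derived. The two stronger readings also conflict: follow-up length can distort a between-arm difference only if the table is split by arm.

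A reader might also infer that the placebo control plays no part in safety. That goes too far. Section 12.5 lists a higher event frequency on drug than in a concurrent or historical control as one ground for possible relatedness, although it specifies no table, population or window. An independent DSMB reviews safety under a Safety Monitoring Plan (sections 9 and 12.4.3) that is not among the documents and may contain displays by arm. Neither supplies the final analysis that section 10.3 should specify.

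Two further objections carry some weight. Section 11 calls the study exploratory and descriptive, and the Synopsis does not name blood pressure or laboratory values as safety variables. But descriptive tables by arm suit a descriptive study, and lesion infections, which the Synopsis does name, have no specified output by arm either. Also, a hearing test that fails at Screening is repeated at later visits (section 6.1; Table 16-1, note 4), so some children may have no pre-dose hearing result. That objection stands and needs a rule.

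**Conclusion.** The point holds as a gap in the specified analysis. For vital signs and laboratory tests, the stated method gives no comparison with placebo. For eye and hearing results, no output is specified. For adverse events and discontinuations, arm and period are left unstated. No data are lost, and neither the design nor the sample size is affected.

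The benefit of correcting it is real but modest. The half-width for a mean difference is about 0.55 SD with 40 v 20 subjects and 0.68 SD with 27 v 13, or about 5.5 and 6.8 mmHg if the SD is 10 mmHg. Every mmHg figure rests on an assumed SD, and every adverse event figure on assumed rates. The follow-up-length distortion, from +15.8 to −17.7 points across the rates shown and close to zero at intermediate crossover, is a conditional illustration of why the window should be fixed. It is not an estimate of bias in the stated plan. The change should be made, but the trial's validity does not depend on it.

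**What to change.** Amend section 10.3 as follows, keeping the listings.

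1. Define treatment-emergent, and set the between-arm safety window as first dose to Week 20 unblinding, with subjects analysed in their randomised arm.
2. Within that window, summarise by arm the change from pre-dose baseline in systolic and diastolic blood pressure, heart rate and oxygen saturation, at each reading over the 2 hours after the first dose and at Weeks 4, 12 and 20.
3. Add Week 20 shift tables by arm for laboratory and eye results. Do the same for hearing only in subjects with a satisfactory pre-dose test, and list the others separately.
4. Present adverse events, lesion infections and discontinuations by arm for the same window.
5. Report open-label sildenafil and off-drug follow-up in separate tables, with subject-weeks as denominator.

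These are descriptive summaries with confidence intervals, not powered tests. The cost is a short text amendment and a few more tables. No visits, procedures or subjects are added. The downside is wide intervals, which should be shown so that the absence of a visible difference is not read as evidence of safety.
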